3.1 Study Equipment Training

486

This phase may begin immediately after enrollment is complete. Participants will be trained and begin using the Control-IQ system to manage their glucose levels and insulin delivery at the conclusion of the training session. Participants will discontinue the use of their existing CGM and insulin pump, if applicable. Training on use of the activity tracker (i.e. Fitbit) will also occur. Participants will use the study equipment (study insulin pump, study CGM, study activity tracker) to collect data for approximately 5 days prior to the Ski Admission. During this at-home portion of the study, participants will be remotely monitored by at least one of their parents or care providers, using the Dexcom or Tandem app.

494

3.1.1 Initiation of CGM

495

The participant will be provided with sensors and instructed to use the study CGM on a daily basis. Training will be provided to participants not experienced with CGM use as to how to use the CGM in real-time to make management decisions and how to review the data after an upload for retrospective review. Participants using a personal CGM prior to the study will discontinue the personal CGM beginning in this period.

500
501

The participant will be observed placing the sensor. The study CGM user's guide will be provided for the participant to take home.

502

3.1.2 Initiation of Study Pump

503

Participants will complete training on the study pump as detailed below.

504
505
506
507
508
509

- The participant will be fully instructed on the study insulin pump. A qualified system trainer (i.e. Certified Diabetes Educator) will conduct the training and in particular discuss differences from their home pump in important aspects such as calculation of insulin on board and correction boluses. Additional topics are not limited to but may include: infusion site initiation, cartridge/priming procedures, setting up the pump, charging the pump, navigation through menus, bolus procedures including stopping a bolus, etc.

510
511
512
513

- The study team will assist the participant in study pump infusion site initiation and will start the participant on the study pump. The study pump will be programmed with the participant's usual basal rates and pump parameters. The participant's personal pump will be removed.

514
515

- The participant will be supervised with the study pump during at least one meal or snack bolus to ensure participant understanding of the pump features.

516
517

- The participant will be encouraged to review the literature provided with the pump and infusion sets after the training is completed.

518

3.1.3 Initiation of Activity Tracker

519
520

Participants will receive a commercially available activity tracker to collect additional information about movement and heart rate. The activity tracker can be removed during bathing.

521

522 **3.1.4 Blood Glucose and Ketone Testing**

523 Participants will receive supplies for blood glucose and ketone testing.

524 • Blood glucose testing

525 ◆ Participants will be provided with a study blood glucose meter and test strips.

526 ◆ All study blood glucose meters will be QC tested with at least two different

527 concentrations of control solution if available during all office visits. A tested meter

528 will not be used in a study if it does not read within the target range at each

529 concentration per manufacturer labeling.

530 ◆ Participants will be reminded to use the study blood glucose meter for all fingerstick

531 BGs during the study.

532 ◆ Participants will be given guidelines for treatment of low or high blood glucose.

533 • Blood ketone testing

534 ◆ Participants will be provided with a study blood ketone meter and test strips.

535 ◆ All study blood ketone meters will be QC tested with at least two different

536 concentrations of control solution if available during all office visits. A tested meter

537 will not be used in a study if it does not read within the target range at each

538 concentration per manufacturer labeling.

539 ◆ Participants will be instructed to perform blood ketone testing as described in

540 section 6.2.4

541 ◆ Participants will be given guidelines for treatment of elevated blood ketones

542 • Participants will be required to have a home glucagon emergency kit. Participants who

543 currently do not have one will be given a prescription for the glucagon emergency kit

544 **3.1.5 Post-Training Check In**

545 The study team will contact the participants approximately 48-72 hours after initiation of the

546 study equipment to discuss:

547 • Questions or concerns about the study and/or equipment

548 • Ensure proper use of study equipment

549 • Ask about the occurrence of any events, including adverse events

550 Members of the study team are available 24 hours a day to address questions or concerns from

551 the participants. Participants will have the contact information of multiple team members. If

552 there is a medical emergency that requires immediate medical attention, participants will be

553 instructed to call emergency medical services (e.g. 911).

554

555

556

Chapter 4: Ski Admission Procedures

557

4.1 Admission Check-In Procedures

558

4.1.1 Participant Check-In & Verification

559 At time of check-in, participants will undergo the following procedures/tests:

- 560 • Vital signs measured
- 561 • A fever or had a significant illness within 24-hours of admission will disqualify
- 562 participant from study
- 563 • A fingerstick blood glucose and fingerstick ketone measurement will be obtained
- 564 • Female subjects of childbearing potential will be required to complete a urine pregnancy
- 565 test. If positive, participant will be discontinued from the study.
- 566 • Study devices and insertion sites will be inspected
- 567 • Confirm that the participant brought his/her personal insulin, study supplies, and regular
- 568 medications.
- 569 • Participants will be asked to perform a blood ketone fingerstick. If ketones >1.5 mmol/L,
- 570 study staff should treat with oral hydration and, if needed, the Glycemic Treatment
- 571 Guidelines will be followed; ketones will be re-checked every hour until ≤1.5 mmol/L.
- 572 The participant will be able to begin participation in the winter sport activities once the
- 573 CGM reads between 80-300 mg/dL and ketones are ≤1.5 mmol/L.
- 574 • Data from the participant's insulin pumps will be reviewed and/or downloaded for a
- 575 review of pump settings and average of daily insulin delivery.

576

4.1.2 Randomization

577 After participants have successfully checked in and are deemed eligible to continue participation
578 in the study, they may be randomized. Using a randomized block design, the participants will be
579 assessed and put in blocks of two according to age and HbA1c. If an identical match is not
580 possible, the closest in age and HbA1c value will be paired and then randomized – one member
581 of each block randomly assigned to each of the two treatment groups.

582 Participants who randomize to Group 1 Hybrid Closed Loop (HCL) will have no modifications
583 to their insulin pump parameters other than the standard 20% reduction in insulin to account for
584 increased exercise while at ski camp. Participants who randomize to Group 2 (MyTDI) will have
585 modifications to their insulin pump parameters to take into consideration his/her total daily
586 insulin along with the 20% reduction in insulin during ski camp.

587 The MyTDI adjustments will be as follows:

- 588 • A single basal rate equal to TDI/48 will be implemented across the whole day
- 589 • A single correction factor of 1650/TDI will be implemented across the whole day

590 • Carbohydrate ratios will be set at:

591 ○ 0000-04:00 CR=450/TDI

592 ○ 0400-1100 CR=450(TDI)/1.2

593 ○ 1100-0000 CR=450/TDI

594 TDI will be reduced by 20% of the internal Control-IQ estimation total daily dose; if not
595 available, total daily dose over the last 5 days will be used.

596 Aside from the insulin pump settings, all other study procedures are identical in the two
597 treatment groups during the Admission and the second at-home portion of the study.

598 **4.2 Main Admission Activities and Procedures**

599 **4.2.1 General Admission Overview**

600 During the entire admission, participants will be monitored remotely by the study team. Study
601 team members trained in all protocol interventions (including the hypo and hyperglycemia safety
602 protocols) will be skiing with the participants, with each member remotely connected to the
603 participants CGM data. In addition, a study team member trained in all protocol and glycemic
604 treatment guidelines procedures will be available at a central location in the resort.

605 All recreational activities will be managed by '*Riding on Insulin*' with study staff supervision.

606 During the overnight hours, study staff will be actively monitoring real-time CGM data for all
607 participants from a dedicated room in the ski resort with direct access to the participants.

608 **4.2.2 Device Procedures for the Participants**

609 All participants will continue to wear the CGM and insulin pump that was provided to them at
610 the Screening Visit throughout the Admission, with the only difference between the randomized
611 groups being the insulin regimen settings in the AP system.

612 Participants will have all equipment with them at all times, including a cell phone (personal or
613 study-provided) with the Dexcom Follow App. Participants will be asked to respond to both
614 hypoglycemia and hyperglycemia alarms. If they do not respond to the alarms within 10
615 minutes, study personnel will assist the subject as per the Glycemic Treatment Guidelines.
616 Participants may be re-educated as needed by the study staff, who will be available at all times to
617 assure proper use of all study equipment.

618 **4.2.3 Participants' Admission Itinerary**

619 Participants will generally follow the below schedule during the Admission:

620 **Evening of Check-in**

621 1500-1900: Check-In & Randomization. Participants will undergo the check-in procedures
622 outlined in section 4.1. Study team will download the study equipment.

623 1900-2000: Dinner. The study CGM will be used to determine the pre-meal bolus.

624 2000-2300: Evening Activity.

625 **Day 1**

626 0800-0900: Breakfast. The study CGM will be used to determine the pre-meal bolus.

627 0900-1200: Morning Ski Activity. Participants will begin the morning ski session if his/her
628 CGM reads >100 mg/dL. If ≤ 100 mg/dL, the Glycemic Treatment Guidelines will be followed
629 until cleared to begin activity.

630 1200-1300: Lunch. The study CGM will be used to determine the pre-meal bolus.

631 1300-1600: Afternoon Ski Activity. Participants will begin the afternoon ski session if his/her
632 CGM reads >100 mg/dL. If ≤ 100 mg/dL, the Glycemic Treatment Guidelines will be followed
633 until cleared to begin activity.

634 1600-1800: Quiet time

635 1800-2000: Dinner. The study CGM will be used to determine the pre-meal bolus.

636 2200: Bedtime Snack. The study CGM will be used to determine the pre-meal bolus.

637 2030-2300: Evening Activity.

638 **Day 2**

639 0800-0900: Breakfast. The study CGM will be used to determine the pre-meal bolus.

640 0900-1200: Morning Ski Activity. Participants will begin the morning ski session if his/her
641 CGM reads >100 mg/dL. If ≤ 100 mg/dL, the Glycemic Treatment Guidelines will be followed
642 until cleared to begin activity.

643 1200-1300: Lunch. The study CGM will be used to determine the pre-meal bolus.

644 1300-1600: Afternoon Ski Activity. Participants will begin the afternoon ski session if his/her
645 CGM reads >100 mg/dL. If ≤ 100 mg/dL, the Glycemic Treatment Guidelines will be followed
646 until cleared to begin activity.

647 1600-1800: Quiet time

648 1800-2000: Dinner. The study CGM will be used to determine the pre-meal bolus.

649 2200: Bedtime Snack. The study CGM will be used to determine the pre-meal bolus.

650 2030-2300: Evening Activity.

651 **Day 3**

652 0800-0900: Breakfast. The study CGM will be used to determine the pre-meal bolus.

653 0900-1200: Checkout and discharge to parents. The study staff will adjust all participants'
654 insulin pumps to remove the 20% rate reduction with the cessation of ski activity and in
655 anticipation of the at-home treatment period. Participants will be discharged if appropriate and
656 in accordance with the Glycemic Treatment Guidelines. Participants will be discharged with the
657 study equipment and any supplies needed for the at-home treatment period.

658 **Chapter 5: At-Home Treatment & Study Completion**

659 **5.1 At-Home Treatment Continuation**

660 Participants discharged from the Ski Admission will continue the randomized treatment for
661 approximately 5 days at home. Participants are free to engage in their normal daily activities and
662 diets during this time. Participants will receive and be instructed to follow the Glycemic
663 Treatment Guidelines during this time. During the at-home continuation portion of the study,
664 participants will be remotely monitored by at least one of their parents or care providers, using
665 the Dexcom or Tandem app.

666 **5.1.1 Post Admission Follow-up Phone Call**

667 The study team will contact the participants approximately 24-48 hours after they are discharged
668 from the Ski Admission to discuss:

- 669 • Questions or concerns about the study and/or equipment
- 670 • Ensure proper use of study equipment
- 671 • Ask about the occurrence of any events, including adverse events

672 Members of the study team are available 24 hours a day to address questions or concerns from
673 the participants. Participants will have the contact information of multiple team members. If
674 there is a medical emergency that requires immediate medical attention, participants will be
675 instructed to call emergency medical services (e.g. 911).

676 **5.2 Final Study Visit**

677 The final study visit may be performed remotely (phone) or in-person. After approximately 5
678 days of at-home use of the study-assigned treatment, participants will be instructed to turn off the
679 Control-IQ system and remove the study equipment. If this visit is performed in person, the
680 participant will return the study equipment to the study team. If this visit is performed remotely,
681 the participant will return the study equipment by mailing it. At this visit, participants will be
682 asked about any existing adverse events and any new adverse events that have not been reported
683 to the study team.

684 **5.3 Early Termination Visit (If Applicable)**

685 Participants will be asked to come for an end of study visit in the event of withdrawal or early
686 termination.

687 **5.4 Unscheduled Visits**

688 Participants may have unscheduled visits during the study period if required for additional device
689 training or other unanticipated needs per the study investigator discretion.

690 **5.5 Participant Access to Study Device at Study Closure**

691 Participant will return all investigational study devices and supplies (insulin pump, CGM,
692 activity tracker, and related supplies) at study closure. Participant may keep the study ketone

UNIVERSITY OF VIRGINIA

693 meter and study glucometer if these devices are not marked for investigational use only after the
694 study team has downloaded all data from the devices.

695

696

Chapter 6: Study Devices

697

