263 23. *IDE#G180053/S008 : “The International Diabetes Closed Loop (iDCL) Trial: Clinical
264 Acceptance of the Artificial Pancreas in Pediatrics - A Pivotal Study of t:slim X2 with Control-
265 IQ Technology”; 4-month parallel group randomized clinical trial with 3:1 randomization to
266 intervention with the closed loop system vs. standard of care (SC); [PENDING REVIEW BY
267 AGENCY]*

268 This trial will test the closed-loop AP system both under home conditions as well as during a
269 stress situation of ski camp while utilizing a new feature, MyTDI, which will be described in
270 more detail in the next section.

271 **1.2 Rationale**

272 The closed-loop AP system works by modulating subcutaneous insulin infusion based on
273 computed real-time needs. Studies have shown that use of an AP system results in increased
274 time in the euglycemic range (70-180 mg/dL), particularly overnight. Challenges persist during
275 times of rapid blood sugar fluctuations, such as following meals or during exercise. Significantly
276 improved glycemic control and fewer hypoglycemic events have been previously demonstrated
277 in pediatric patients using the AP system in summer and winter camp settings. Studies to date
278 have run the system using the foundation of the subject's home insulin parameters, which are
279 often complicated and involve fluctuating basal rates, carbohydrate ratios, and correction factors
280 depending on the time of the day and might not be reflective of his/her true insulin needs. The
281 CLC system allows the user to receive feedback on his/her average total daily insulin needs with
282 a report of Total Daily Insulin (TDI). Clinicians can in turn use TDI to easily determine insulin
283 pump parameters using standard formulas to calculate the optimal basal rate, carbohydrate ratio,
284 and correction factor as follows:

- 285 • Basal rate = TDI/48 (half of the daily insulin needs are delivered in the form of basal
286 insulin)
- 287 • Correction factor (CF) = 1650/TDI
- 288 • Carb ratio (CR) = 450/TDI (to be used for lunch and dinner)
- 289 • Carb ratio for breakfast: to achieve a 20% increase in insulin we will use the following
290 carb ratio: $CR_{bkfst} = CR/1.2$ (to account for increased insulin needs in the morning)

291 The system can then modify the insulin to keep blood glucose in range as necessary.

292 This trial aims to demonstrate the safety and feasibility of using MyTDI to determine insulin

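### Section 4.1.2 prints the MyTDI 0400-1100 carbohydrate ratio with TDI in the numerator, contradicting section 1.2 and nearly removing the breakfast bolus if followed

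*Combined protocol and SAP*

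**What the plan says.** Section 1.2 (Rationale) sets out how pump parameters follow from total daily insulin (TDI). The base ratio is "Carb ratio (CR) = 450/TDI (to be used for lunch and dinner"). For breakfast it continues: "Carb ratio for breakfast: to achieve a 20% increase in insulin we will use the following" "carb ratio: $CR_{bkfst} = CR/1.2$ (to account for increased insulin needs in the morning").

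Section 4.1.2 (Randomization) turns this into the settings for Group 2, in three clock blocks. The first block, midnight to 0400, uses 450/TDI. The last reads "1100-0000 CR=450/TDI". The middle block, which covers breakfast, reads "0400-1100 CR=450(TDI)/1.2".

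The same section fixes the TDI that enters these formulas at camp: "TDI will be reduced by 20% of the internal Control-IQ estimation total daily dose; if not" available, the total daily dose over the last 5 days is used. At discharge on Day 3 (section 4.2.3) the 20% reduction is removed, and the assigned treatment continues for about 5 days at home (section 5.1).

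**The concern.** In the middle block TDI multiplies, where section 1.2 and the two neighbouring blocks have it divide. A carbohydrate ratio is grams covered by one unit, so a larger ratio means less insulin. The printed form therefore moves the breakfast dose in the opposite direction to the stated purpose.

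The position of the line matters. Section 1.2 is background. Section 4.1.2 is the operative list and the only place that gives the clock times, so anyone programming a Group 2 pump has to work from it. The settings are also the whole experimental contrast: section 4.2.2 says that during the admission the only difference is between the "groups being the insulin regimen settings in the AP system". The 0400-1100 block contains the scheduled camp breakfast on Days 1, 2 and 3 ("0800-0900: Breakfast. The study CGM will be used to determine the pre-meal bolus", section 4.2.3), and it applies again on the mornings at home. Section 10.2 frames the primary hypothesis on time in 70-180 mg/dL during home use. A wrong morning ratio would therefore bear on both participant safety and the primary comparison.

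**Working it through.** **Inputs from the protocol.** Base ratio CR = 450/TDI and breakfast ratio CR/1.2 (section 1.2); printed 0400-1100 ratio 450(TDI)/1.2 (section 4.1.2); camp TDI = 0.8 × the estimated total daily dose (section 4.1.2).

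**Assumptions, not in the protocol.** A full TDI of 50 U/day as the example, with a range of 30 to 80, and a 60 g breakfast.

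**Step 1: reproduce section 1.2.** (450/TDI)/1.2 = 375/TDI. Insulin per gram is the reciprocal of the ratio, so breakfast against base is (TDI/375)/(TDI/450) = 450/375 = 1.20. This is the stated 20% increase, so section 1.2 is internally consistent.

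**Step 2: evaluate the printed line.** 450 × TDI/1.2 = 375 × TDI.

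**Step 3: compare.** (375 × TDI)/(375/TDI) = TDI².

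| TDI used (U/day) | Printed (g/U) | Intended (g/U) | Printed/intended |
|---|---|---|---|
| 30 (full) | 11,250 | 12.5 | 900 |
| 50 (full) | 18,750 | 7.5 | 2,500 |
| 80 (full) | 30,000 | 4.69 | 6,400 |
| 24 (camp, 0.8 × 30) | 9,000 | 15.63 | 576 |
| 40 (camp, 0.8 × 50) | 15,000 | 9.375 | 1,600 |
| 64 (camp, 0.8 × 80) | 24,000 | 5.86 | 4,096 |

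**Step 4: convert to a dose.** For 60 g of carbohydrate at camp TDI 40:
- intended: 60/9.375 = 6.4 U
- base ratio: 450/40 = 11.25 g/U, so 60/11.25 = 5.33 U
- as printed: 60/15,000 = 0.004 U

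**Step 5: a plausible wrong repair.** The line does not show where the lost division belongs. Grouped as (450/TDI)/1.2, it gives 375/TDI. Grouped as 450/(TDI/1.2), it gives 540/TDI. At camp TDI 40 the second is 540/40 = 13.5 g/U, and 60/13.5 = 4.44 U. That is (6.4 − 4.44)/6.4 = 31% below the intended dose and also below the base dose of 5.33 U. The second grouping is an inference about how the line might be misread. Nothing in the protocol suggests that anyone has done so.

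**The case against.** The best reply is that this is a misprint with only one sensible reading. Section 1.2 gives the right formula, its purpose and its direction, and the lines above and below print 450/TDI. A ratio in the thousands beside neighbouring ratios of about 6 to 19 g/U (450/TDI for TDI from 80 down to 24) would hardly be entered unnoticed, and the larger the factor, the less likely it is that anyone would follow the line. This stands, and it is why the practical risk is low and the multiples are not a forecast of harm.

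Safeguards would also limit the effect of an under-bolus. The system raises insulin automatically and issues a High Alert above 200 mg/dL (section 6.2.4). Staff monitor CGM throughout the admission (section 4.2.1) and step in if alarms go unanswered for 10 minutes (section 4.2.2). The dose comparison counts only the carbohydrate bolus and ignores automated correction. These points bound the consequence but do not correct the setting. The pump-settings review in section 4.1.1 takes place at check-in, before randomization, so it does not check the newly programmed MyTDI values. At home, remote monitoring is by parents or care providers (section 5.1).

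Finally, the text was machine-read, so a lost slash could be an extraction fault. This cannot be fully excluded. However, the adjacent lines kept their slashes, this line kept its second one, and its parentheses enclose only TDI, so a misprint in the source is more likely.

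**Conclusion.** The concern holds. The operative list of MyTDI settings contains a formula that is wrong as written and contradicts section 1.2, and no other section corrects it. The printed ratio exceeds the intended one by TDI squared: 576 to 4,096 times at camp and 900 to 6,400 times at full TDI, for an assumed full TDI of 30 to 80 U/day. Followed literally, it nearly abolishes a bolus that was meant to rise by 20%. The contradiction itself is algebraic and needs no assumption; only the worked sizes rest on the assumed TDI values and the 60 g meal. The point needs correcting because of what the line is, a dosing instruction for the experimental arm in adolescents, and not because harm from the literal value is likely.

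**What to change.** Check the 0400-1100 line in the protocol source file. If it reads as shown here, replace it with CR = (450/TDI)/1.2 = 375/TDI, parentheses included, to agree with section 1.2. A worked example beside it would rule out the wrong grouping: TDI 50 gives 7.5 g/U. Then compare each Group 2 participant's programmed 0400-1100 ratio with 375/TDI, using the TDI in force at the time: reduced by 20% at camp, unreduced after discharge.

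The cost is a one-line protocol correction and a short check of pump settings in one arm. Design, sample size and analysis are unaffected.
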